8.0 Risks - Benefits to participating to the study

The results of the salivary tests will be communicated at the end of the study period to the participants. There is no direct benefit for participants, and we are hoping they will gain a great awareness of better understanding this urgent public health issue for young children. The indirect effects to keep primary schools open even in case of red code are all the benefits for children to attend school and the positive impact on society such as facilitating parents' working especially in case of lockdown when teleworking is extremely challenging for parents looking after young children. Depending on results, this study could provide reassuring data concerning teachers' work conditions.

All Children of participating schools will receive once a week a healthy snack to thank them for participation to the study.

9.0 Ethics

9.1 Declaration of Helsinki and ICH Guidelines for Good Clinical Practice (GCP)

Study investigators will ensure that this study is conducted according to the principles of the latest revision of the Declaration of Helsinki and in full conformity with the ICH Good Clinical Practice (GCP) and local regulatory requirements.

9.2 Informed consent

Written, informed consent must be obtained from all participants (inform assent for children) and their parents (or legal guardians) for children before a participant can be included in the present study.

9.3 Ethics committee and regulatory agency review

The protocol proposed Inform consent form (ICF), and all other study documents, will be submitted to the local ethics committee “Commission d’Ethique hospitalo -facultaire des Cliniques universitaires St-Luc - UCLouvain” in Brussels for approval. The Principal Investigator will submit and, where necessary, obtain approval from the EC for all subsequent substantial amendments to the protocol and ICF.

9.4 Subject confidentiality

This study will be carried out in accordance with the law (July 30, 2018) on the use and processing of sensitive data, the law of patient’s right (August 22, 2002) and the general European regulation on the protection of personal data (May 25, 2018). Identity and participation of patients to the survey will remain strictly confidential.

The manager of confidential data will be Pr. [name].

All data will be coded: a unique study number containing no personally identifiable information (PII) will identify each subject, and, will be used in the questionnaire, database and sampling. A separate confidential file containing PII will be stored in a secured (locked) location in accordance with data protection requirements. Only the study investigators, the EC and regulatory authorities will have access to the records.

No participant name will be mentioned on samples. A sequential identification number will be automatically allocated to each participant enrolled in the study. This number will identify the participant and will be composed of 12 digits:

- a two-digits number allocated to the school he/she is attending and the replacement if the first school stop for any reason
- a two-digits number allocated to the class, with a first digit for the grade, or 9 for adults outside the class) and a second digit numbering classes within each grade
- a two-digits serial number within the class he/she is in, and above 50 for teachers in charge of the class
- a two-digits sequential number corresponding to adults linked to the child
- a two digits control number (such as modulo 89 of the 8 first digits)
- a two-digits number corresponding to the calendar week of data collection

This unique and automatically checked IDs will allow parents or guardians to enter on a website with a unique password they will receive with ID, in order to fill data for their child. Each child will receive a paperback diary for daily activities and all these books will be collected at the end of the study. Information in the paperback notebooks will be entered after the study in case of no internet access for parents or French problems.

The date of birth of the participant will be mentioned on the sample along with his/her ID number.

The online questionnaires will only be accessible with a login and a password respecting the standards of complexity related to passwords. The data collected will be anonymised. Only the investigators of the study will be aware of the link between the different questions and the participants. The server is hosted by a computing infrastructure at UCLouvain, which is configured to update automatically. The physical location of the server is in the IT manager's office. Access to the said office is limited and secure. Backups of data encoded on the server will be encrypted on an external drive. No remote access will be allowed to the server.

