Study participants/numbers of participating schools	
All Belgian primary schools of the Federation Wallonie – Bruxelles that have organized a full resumption of school activities with the control measures recommended by the government, are eligible for the study.
 
Inclusion criteria All children and school attenders from selected schools will be invited to participate.
 
Exclusion criteria Refusal to provide written informed consent before enrolment
 
Sampling procedure Each participating primary school will be considered as a cluster. Eight schools will be chosen by purposive sampling on three criteria: either high (≥ 2 classes per grade) or low size of the school, a school within an area with either a high or a low incidence of SARS-CoV-2 during April 2020, the first wave of covid-19 in Belgium, and a school with either a high or a low socioeconomic level (Belgian 20-point-scale ISE index >14 or <6). As direct partners in the project, physicians in charge of health promotion in schools (PSE teams) will select schools.

Study description	
Inclusion visit All participants (children and adults school attenders) will be tested at the inclusion day with
 
 - A salivary SARS-CoV2 test - A rapid serological test by finger prick (AVIOQ[®]) to determine the seroprevalence of SARS-CoV-2 
All participants (children and adults school attenders) will be invited to fill a questionnaire on an electronic format when possible or with a paperback part if not, depending on parents' convenience.
 
Follow-up visits During six consecutive weeks, all participants will be tested once a week with a salivary test. During six consecutive weeks, all participants will be invited to complete a follow-up questionnaire to assess any symptom compatible with a SARS-CoV-2 infection or a contact with a confirmed SARS-CoV-2 case or a travelling return from a risk area.

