4.3 Selection of participating schools

All Belgian primary schools of the Federation Wallonie – Bruxelles that have organized a resumption of school activities with the social control measures recommended by the government, are eligible for the study. All children and school attenders attending included schools will be eligible to participate.

Each participating school will be considered as a statistical cluster because children within a school share more correlation together than with children from other schools (children are not an independent and identically distributed (i.i.d.) sample) and an intraclass coefficient (ICC) of 9% will be used in analysis.

We will enrol schools according to the following three criteria:

- School size: small school versus a large one

- Incidence of Sars-CoV-2 infection during the first wave of the pandemic in April 2020
 - Regions/cities with a low incidence (from 1.5 to 4.9 per thousand inhabitants on May 6th, 2020)
 - Regions/cities with a high incidence (from 5.0 to 7.5 per thousand inhabitants on May 6th, 2020)
- Socio-economic level of the school: low socio-economic level versus high level, based on ISE that is an official Belgian 20-point-scale index for all schools of the Federation Wallonie-Bruxelles (FWB).

Crossing those three criteria leads to eight categories of schools and one school of each category will be sampled

- Small school - very low incidence city - low socio-economic level
- Small school - very low incidence city - high socio-economic level
- Small school - very high incidence city - low socio-economic level
- Small school - very high incidence city - high socio-economic level
- Large school - very low incidence city - low socio-economic level
- Large school - very low incidence city - high socio-economic level
- Large school - very high incidence city - low socio-economic level
- Large school - very high incidence city - high socio-economic level

According to the definition of the FWB, investigators consider a small school a school with less than 300 children enrolled in the school and a large one a school with more than 300 children.

To determine regions with the highest and lowest incidence of SARS-CoV-2 infection during the first pandemic wave in Belgium investigators will refer to the epidemiological reports of Sciensano: <https://covid-19.sciensano.be/fr/covid-19-situation-epidemiologique>

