4.4.3 Definitions

4.4.3.1 Asymptomatic versus symptomatic cases

- A positive case: a participant who has a positive PCR salivary test for SARS-CoV-2 detected by systematic weekly screening
- Asymptomatic case: a participant who has a positive salivary test for SARS-CoV-2 during the study period and who did not declare any symptoms compatible with COVID-19
- Symptomatic case: a participant who has a positive salivary test with symptoms compatible with COVID-19 during the study period

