5.1 Inclusion day

All participants, children and adults school attenders, will be tested at the inclusion day with

- a salivary SARS-CoV2 PCR test collected in the school, under investigators supervision
- a rapid serological test by finger prick (AVIOQ[®]) to determine the seroprevalence of SARS-CoV-2
- All participants (children and adult school attenders) will be invited to complete an electronic questionnaire when possible and a paperback questionnaire otherwise.

The questionnaire will address the following information (see attached file) partially inspired of the questionnaire used in the prevalence study *“Prevalence and incidence of antibodies against SARS-COV-2 in children measured for one year in Belgium: a sero-epidemiological prospective cohort study”* (study coordinator: [name], Sciensano).

- Socio-demographic data: gender, birth date, home postal code, a contact email address, a contact mobile number, country of birth of child and parents
- Housing information: number of people in the household, number of siblings, number of sleeping rooms, distance between school and home
- Exposition information: pre- and after-school daycare attending, extracurricular activities, parent's profession, transportation means between home and school

The salivary SARS-CoV2 sample will be performed at school by the participant him or herself under the supervision of the subinvestigators (80 medical students on contract) for minor

participants. An explanatory film on the method of self-performing the saliva sample will be provided to participants. The children and the teachers will use a garling method to produce saliva. The full procedure is explained in the explanatory film. The participant will wear an adapted mask while gargling. A full explanation of the used gargling sampling technic is also well detailed in the attached paper (19)

The procedure will be performed in a well-ventilated space one participant at a time. The medical student who will collect the sample will wear adapted personal protective equipment (PPE) in order to reduce the risk of transmission to as good as 0. The PPE will include FFP2 mask, gloves, glasses and a protective gown.

After collection, salivary samples will be transported to one of the three participating laboratories (UCLouvain - ULiège - ULB) by the medical student.

Teachers of each class will be invited to complete a questionnaire once with the following questions

- Number of children in the classroom

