5.2 Follow-up visit

All participants, children attending selected schools and adults school attenders, will be asked to provide a weekly salivary specimen for six consecutive weeks.

All participants, children attending selected schools and adult school attenders, will have to complete a follow-up questionnaire, once a week for six consecutive weeks (See attached file) providing information about

- any compatible symptom with a SARS-CoV-2 infection
- a high-risk contact with a confirmed SARS-CoV-2 case

- social contacts (number of contacts during the last 7 days outside the school environment and outside the household, including travelling abroad)

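### Follow-up data reach the study by two routes with different timing and no check on capture mode, so cases can be misclassified and, if paper use differs by socio-economic level, that school contrast could be distorted

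*Combined protocol and SAP*

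**What the plan says.** - **Default route.** Section 9.4 gives parents or guardians an ID and password for a website "in order to fill data for their child".
- **Notebook.** The same section states that "Each child will receive a paperback diary for daily activities and all these books will be collected at the end of the study". It continues: "Information in the paperback notebooks will be entered after the study in case of no internet access for parents or French problems". It does not say what happens to the other families' books.
- **Follow-up items.** Under section 5.2 all participants "will have to complete a follow-up questionnaire, once a week for six consecutive weeks". It covers compatible symptoms, high-risk contact with a confirmed case, and social contacts outside school and household. Whether it is electronic or on paper is not stated.
- **Inclusion questionnaire.** This one does have a paper version: participants "will be invited to complete an electronic questionnaire when possible and a paperback questionnaire otherwise" (section 5.1). The synopsis offers it "with a paperback part if not, depending on parents' convenience".
- **Case definition.** In section 4.4.3.1 an asymptomatic case is a participant with a positive salivary test "who did not declare any symptoms compatible with COVID-19".
- **Endpoints.** In section 3.4 the child-to-child and child-to-adult endpoints both require an asymptomatic infecting child. The synopsis keeps that condition only for child-to-adult.
- **School contrast.** One of the three selection criteria in section 4.3 is "Socio-economic level of the school: low socio-economic level versus high level". Section 7.1 compares incidence and secondary attack rates between three kinds of schools. It names no capture-mode variable, completeness table or rule for missing reports.

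**The concern.** For follow-up, the notebook is the only fallback the documents describe for a family that cannot use the website. It is handed in once, after the six weeks, so a gap cannot be seen or queried while the study runs. One unreturned book loses 6 of 6 weekly reports, where one missed weekly form loses 1 of 6.

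A missing report is not neutral here. Under the case definition, a positive child for whom nothing was declared falls into the asymptomatic group, and two endpoints are built on that group. Reported contacts also help to decide whether an infection came from outside school. Sequencing cannot be counted on to settle the source: section 3.3 makes it exploratory, subject to resources, and limited to samples with a Ct below 30.

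If the capture route were also related to the school's socio-economic level, an error that differs by route would appear as a difference between schools. Enrolling more children would not remove it.

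**Working it through.** **1. The plan's own figures.** The plan gives no figure on this point. Its expected number of children (section 7.1) reproduces: 4 × 200 + 4 × 400 = 2400. The eight-category design in section 4.3 puts two small and two large schools at each socio-economic level, so 2 × 200 + 2 × 400 = 1200 children in four schools per level.

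**2. What the notebook can be.** Section 9.4 describes it as a diary of daily activities, and section 5.2 assigns symptoms and contacts to the weekly questionnaire. There are two readings:
- The notebook carries the website items. Then offline families report those items by a route with different timing from everyone else's.
- The notebook records activities only. Then no route is stated by which offline families return follow-up symptoms and contacts.

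The text needs changing under either reading.

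**3. Illustration: reported outside source.** Every input is an assumption; none is in the documents.
- Paper share: pH = 0.05–0.10 in high and pL = 0.20–0.50 in low socio-economic schools.
- Share of books unusable: u = 0.20–0.40, the same in both.
- Share of infections with a reportable outside contact: f = 0.5 in both.
- Missing data are read as no outside contact.

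Missing share = p × u:
- High: 0.05 × 0.20 = 1% to 0.10 × 0.40 = 4%, or 12–48 of 1200 children.
- Low: 0.20 × 0.20 = 4% to 0.50 × 0.40 = 20%, or 48–240 of 1200.

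Reported outside share = f × (1 − p × u), so the gap = f × u × (pL − pH):
- Smallest: 0.5 × 0.20 × (0.20 − 0.10) = 0.01, i.e. 49% against 48%.
- Largest: 0.5 × 0.40 × (0.50 − 0.05) = 0.09, i.e. 49% against 40%.

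**4. Illustration: observed asymptomatic share.** Again all inputs are assumed. Let s be the true symptomatic share among positives (0.3 or 0.5, equal in both levels), p the paper share (0.10–0.40 low, 0.02–0.05 high), and c the probability that true symptoms are captured.

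Observed asymptomatic share = 1 − s × [(1 − p) × c_web + p × c_paper], so low minus high = s × (c_web − c_paper) × (pL − pH).
- c_web 0.9, c_paper 0.7, s 0.3, shares 0.10 and 0.02: 0.3 × 0.2 × 0.08 = 0.005, or 0.5 points.
- c_web 0.9, c_paper 0.5, s 0.5, shares 0.40 and 0.05: 0.5 × 0.4 × 0.35 = 0.07, or 7 points.
- Equal capture (0.9 in both): 0.
- Equal paper use (0.20 in both): 0.
- Notebook better than website (0.9 against 0.7): −0.5 points (0.3 × −0.2 × 0.08) to −3.5 points (0.5 × −0.2 × 0.35).

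The sign depends on which route captures more and on where paper is used more. The documents settle neither.

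**The case against.** A reader might infer that families in low socio-economic schools will supply worse data and that school transmission will therefore look higher there. The documents do not support that:
- Nothing ties lack of internet or difficulty with French to the socio-economic index, and no paper share is given. The synopsis lets parents choose paper at inclusion for convenience, so paper users need not be a deprived group.
- Nothing shows that the notebook is the poorer instrument. A diary kept daily may involve less recall error than a weekly form.
- No rule says that a missing contact report means no outside contact. Such a case could be classed as of unknown source.
- A spurious gap of about 10 points can be reached only by pairing 20% unusable books in high with 40% in low socio-economic schools (49.5% against 40%). With the same loss in both, the ceiling is 9 points.

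The website's advantage should not be overstated either. Section 9.4 describes automatic checks on IDs, not on answers, and no reminders are described for online families. Inclusion exposure data do not depend on the notebook.

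There is also a partial safeguard. Under section 5.0 the school health team interviews absent participants about a possible link with infection, until two weeks after study end. This reaches children kept at home for symptoms or a high-risk contact, whatever their internet access. It is triggered by absence, however, and salivary results are withheld during the study, so a positive child who stays in class can be missed. Those are the children on whom the asymptomatic-infector endpoints rest.

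What stands of the objection is that size, direction and the link to socio-economic level are unknown. It does not remove the two routes, the late collection or the absence of any check.

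**Conclusion.** The point holds as a weakness in data capture that can misclassify cases. It is not a demonstrated socio-economic bias. Four features rest on the text: notebooks are collected only at the end; their entry is described only for families without internet or with French difficulties; an undeclared symptom makes a positive participant asymptomatic; and the analysis does not look at capture mode. That the notebook stands in for the weekly questionnaire is a reasonable inference, but it is not written.

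An effect on the socio-economic contrast requires both that paper use differs between school types and that the two routes capture differently. On the assumed inputs this gives about 1–9 points in reported outside source. For asymptomatic share it gives 0.5–7 points if the notebook is worse, and −0.5 to −3.5 if it is better. These show the order of magnitude under stated assumptions and are not estimates. The change is worth making before the first school starts, because capture mode and missed weeks cannot be reconstructed reliably afterwards.

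**What to change.** - **Sections 5.2 and 9.4:** state the mode of the weekly follow-up questionnaire and the content of the notebook. For families not reporting online, have the medical students who already supervise the weekly saliva round collect a one-page paper form with the same items as the website. Label it with the participant ID, which already contains the calendar week. Provide translation or language help where needed, since an identical French form does not help families who have difficulty with French.
- **Section 9.4:** apply one diary-entry rule to all children, regardless of internet access or infection status. Entering diaries only for cases and their classmates would make data availability depend on the outcome.
- **Section 4.4.3.1:** classify a positive participant with a missing weekly report as of unknown symptom status, not asymptomatic.
- **Section 7.1:** record capture mode (web or paper) for each weekly report, tabulate completeness by mode and socio-economic level, and add a sensitivity analysis by mode.

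The cost is slightly more handling at each saliva round, modest data entry and some translation. No additional visits are needed.

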10.0 Samples storage and biobank

Saliva samples, sera and remains of these collected samples will be stored after consent in biobanks.

The biological materials will be stored in the biobank of each participating lab where samples will be analysed. Documentation and location of each collected material and its remain after analysis will be performed at the site of the biobank. The manager of the UCLouvain biobank is [name] who is responsible for it.

As mentioned, saliva samples will be used to perform a rt-PCR for SARS-CoV-2. Any positive sample will be analysed for viral phylogenetic purposes. All samples will be stored at -80°C, according to the procedure for viral particles preservation. All samples and remains will be held in the biobank for 15 years.

All patients or their parents/tutor will be informed on the sample use and storage. They will also be informed on the strict confidentiality of any patient data and will be assured that all samples will be anonymized.

11.0 Financial and Insurance

This study will be financially supported by research funds of FWB.

The involved parties will be insured, in accordance with the Belgian law 2004022376 “*Loi relative aux expérimentations sur la personne humaine du 7 mai 2004 et mises à jour au 16-11-2018*,” against financial loss resulting from personal injury and/or other damages, which may arise as a consequence of this study.

